### **5.5.2 Prohibited Concomitant Medications**

Subjects are prohibited from receiving the following therapies during the Screening and Treatment Phase (including retreatment for post-complete response relapse) of this trial:

- Antineoplastic systemic chemotherapy or biological therapy
- Immunotherapy not specified in this protocol
- Chemotherapy not specified in this protocol
- Investigational agents other than pembrolizumab
- Live vaccines within 30 days prior to the first dose of trial treatment and while participating in the trial. Examples of live vaccines include, but are not limited to, the following: measles, mumps, rubella, varicella/zoster, yellow fever, rabies, BCG, and typhoid vaccine.
- Systemic glucocorticoids for any purpose other than to modulate symptoms from an event of clinical interest of suspected immunologic etiology. The use of physiologic doses of corticosteroids may be approved after consultation with the Sponsor.

Subjects who, in the assessment by the investigator, require the use of any of the aforementioned treatments for clinical management should be removed from the trial. Subjects may receive other medications that the investigator deems to be medically necessary.

The Exclusion Criteria describes other medications which are prohibited in this trial.

There are no prohibited therapies during the Post-Treatment Follow-up Phase.

## **5.6 Rescue Medications & Supportive Care**

### **5.6.1 Supportive Care Guidelines**

Subjects should receive appropriate supportive care measures as deemed necessary by the treating investigator. Suggested supportive care measures for the management of adverse events with potential immunologic etiology are outlined below. Where appropriate, these guidelines include the use of oral or intravenous treatment with corticosteroids as well as additional anti-inflammatory agents if symptoms do not improve with administration of corticosteroids. Note that several courses of steroid tapering may be necessary as symptoms may worsen when the steroid dose is decreased. For each disorder, attempts should be made to rule out other causes such as metastatic disease or bacterial or viral infection, which might require additional supportive care. The treatment guidelines are intended to be applied when the investigator determines the events to be related to pembrolizumab.

Note: if after the evaluation the event is determined not to be related, the investigator does not need to follow the treatment guidance (as outlined below). Refer to Section 5.2.1 for dose modification.

It may be necessary to perform conditional procedures such as bronchoscopy, endoscopy, or skin photography as part of evaluation of the event.

- **Pneumonitis:**

- For **Grade 2 events**, treat with systemic corticosteroids. When symptoms improve to Grade 1 or less, steroid taper should be started and continued over no less than 4 weeks.
- For **Grade 3-4 events**, immediately treat with intravenous steroids. Administer additional anti-inflammatory measures, as needed.
- Add prophylactic antibiotics for opportunistic infections in the case of prolonged steroid administration.
- If grade 2 or higher pneumonitis occurs in patients receiving concurrent radiation therapy to the chest, radiation therapy will be suspended immediately.

- **Diarrhea/Colitis:**

Subjects should be carefully monitored for signs and symptoms of enterocolitis (such as diarrhea, abdominal pain, blood or mucus in stool, with or without fever) and of bowel perforation (such as peritoneal signs and ileus).

- All subjects who experience diarrhea/colitis should be advised to drink liberal quantities of clear fluids. If sufficient oral fluid intake is not feasible, fluid and electrolytes should be substituted via IV infusion. For Grade 2 or higher diarrhea, consider GI consultation and endoscopy to confirm or rule out colitis.
- For **Grade 2 diarrhea/colitis**, administer oral corticosteroids.
- For **Grade 3 or 4 diarrhea/colitis**, treat with intravenous steroids followed by high dose oral steroids.
- When symptoms improve to Grade 1 or less, steroid taper should be started and continued over no less than 4 weeks.
- When grade 3 or higher diarrhea or colitis occurs in a patient receiving concurrent radiation therapy to the abdomen or pelvis and the bowel is receiving radiation, then the radiation therapy will be suspended immediately.

- **Type 1 diabetes mellitus (if new onset, including diabetic ketoacidosis [DKA]) or  $\geq$  Grade 3 Hyperglycemia, if associated with ketosis (ketonuria) or metabolic acidosis (DKA)**

- For **T1DM or Grade 3-4 Hyperglycemia**
  - Insulin replacement therapy is recommended for Type I diabetes mellitus and for Grade 3-4 hyperglycemia associated with metabolic acidosis or ketonuria.

- Evaluate patients with serum glucose and a metabolic panel, urine ketones, glycosylated hemoglobin, and C-peptide.
- **Hypophysitis:**
  - For **Grade 2** events, treat with corticosteroids. When symptoms improve to Grade 1 or less, steroid taper should be started and continued over no less than 4 weeks. Replacement of appropriate hormones may be required as the steroid dose is tapered.
  - For **Grade 3-4** events, treat with an initial dose of IV corticosteroids followed by oral corticosteroids. When symptoms improve to Grade 1 or less, steroid taper should be started and continued over no less than 4 weeks. Replacement of appropriate hormones may be required as the steroid dose is tapered.
- **Hyperthyroidism or Hypothyroidism:**

Thyroid disorders can occur at any time during treatment. Monitor patients for changes in thyroid function (at the start of treatment, periodically during treatment, and as indicated based on clinical evaluation) and for clinical signs and symptoms of thyroid disorders.

  - **Grade 2** hyperthyroidism events (and **Grade 2-4** hypothyroidism):
    - In hyperthyroidism, non-selective beta-blockers (e.g. propranolol) are suggested as initial therapy.
    - In hypothyroidism, thyroid hormone replacement therapy, with levothyroxine or liothyroinine, is indicated per standard of care.
  - **Grade 3-4** hyperthyroidism
    - Treat with an initial dose of IV corticosteroid followed by oral corticosteroids. When symptoms improve to Grade 1 or less, steroid taper should be started and continued over no less than 4 weeks. Replacement of appropriate hormones may be required as the steroid dose is tapered.
- **Hepatic:**
  - For **Grade 2** events, monitor liver function tests more frequently until returned to baseline values (consider weekly).
    - Treat with IV or oral corticosteroids
  - For **Grade 3-4** events, treat with intravenous corticosteroids for 24 to 48 hours.
  - When symptoms improve to Grade 1 or less, a steroid taper should be started and continued over no less than 4 weeks.
- **Renal Failure or Nephritis:**
  - For **Grade 2** events, treat with corticosteroids.
  - For **Grade 3-4** events, treat with systemic corticosteroids.

- When symptoms improve to Grade 1 or less, steroid taper should be started and continued over no less than 4 weeks.
- **Management of Infusion Reactions:** Signs and symptoms usually develop during or shortly after drug infusion and generally resolve completely within 24 hours of completion of infusion.

Table 3 below shows treatment guidelines for subjects who experience an infusion reaction associated with administration of pembrolizumab (MK-3475).

Table 3 Infusion Reaction Treatment Guidelines

NCI CTCAE Grade	Treatment	Premedication at subsequent dosing
Grade 1 Mild reaction; infusion interruption not indicated; intervention not indicated	Increase monitoring of vital signs as medically indicated until the subject is deemed medically stable in the opinion of the investigator.	None
Grade 2 Requires infusion interruption but responds promptly to symptomatic treatment (e.g., antihistamines, NSAIDS, narcotics, IV fluids); prophylactic medications indicated for <=24 hrs	
Stop Infusion and monitor symptoms. Additional appropriate medical therapy may include but is not limited to:
 
IV fluids Antihistamines NSAIDS Acetaminophen Narcotics
 
Increase monitoring of vital signs as medically indicated until the subject is deemed medically stable in the opinion of the investigator.
 
If symptoms resolve within one hour of stopping drug infusion, the infusion may be restarted at 50% of the original infusion rate (e.g., from 100 mL/hr to 50 mL/hr). Otherwise dosing will be held until symptoms resolve and the subject should be pre-medicated for the next scheduled dose.
 
Subjects who develop Grade 2 toxicity despite adequate premedication should be permanently discontinued from further trial treatment administration.
	
Subject may be premedicated 1.5h (<math>\pm</math> 30 minutes) prior to infusion of pembrolizumab (MK-3475) with:
 
Diphenhydramine 50 mg po (or equivalent dose of antihistamine).
 
Acetaminophen 500-1000 mg po (or equivalent dose of antipyretic).

Grades 3 or 4  Grade 3: Prolonged (i.e., not rapidly responsive to symptomatic medication and/or brief interruption of infusion); recurrence of symptoms following initial improvement; hospitalization indicated for other clinical sequelae (e.g., renal impairment, pulmonary infiltrates)  Grade 4: Life-threatening; pressor or ventilatory support indicated	
Stop Infusion. Additional appropriate medical therapy may include but is not limited to:
 
IV fluids Antihistamines NSAIDS Acetaminophen Narcotics Oxygen Pressors Corticosteroids Epinephrine
 
Increase monitoring of vital signs as medically indicated until the subject is deemed medically stable in the opinion of the investigator.
 
Hospitalization may be indicated.
 
Subject is permanently discontinued from further trial treatment administration.
	No subsequent dosing
Appropriate resuscitation equipment should be available in the room and a physician readily available during the period of drug administration.		

## 5.7 Diet/Activity/Other Considerations

### 5.7.1 Diet

Subjects should maintain a normal diet unless modifications are required to manage an AE such as diarrhea, nausea or vomiting.

### 5.7.2 Contraception

Pembrolizumab may have adverse effects on a fetus in utero. Furthermore, it is not known if pembrolizumab has transient adverse effects on the composition of sperm.

For this trial, male subjects will be considered to be of non-reproductive potential if they have azoospermia (whether due to having had a vasectomy or due to an underlying medical condition).

Female subjects will be considered of non-reproductive potential if they are either:

- (1) postmenopausal (defined as at least 12 months with no menses without an alternative medical cause; in women <45 years of age a high follicle stimulating hormone (FSH) level in the postmenopausal range may be used to confirm a post-menopausal state in women not using hormonal contraception or hormonal replacement therapy. In the absence of 12 months of amenorrhea, a single FSH measurement is insufficient.);

OR

- (2) have had a hysterectomy and/or bilateral oophorectomy, bilateral salpingectomy or bilateral tubal ligation/occlusion, at least 6 weeks prior to screening;

OR

- (3) has a congenital or acquired condition that prevents childbearing.

Female and male subjects of reproductive potential must agree to avoid becoming pregnant or impregnating a partner, respectively, while receiving study drug and for 120 days after the last dose of study drug by complying with one of the following:

- (1) practice abstinence† from heterosexual activity;

OR

- (2) use (or have their partner use) acceptable contraception during heterosexual activity.

Acceptable methods of contraception are‡:

Single method (one of the following is acceptable):

- intrauterine device (IUD)
- vasectomy of a female subject's male partner
- contraceptive rod implanted into the skin

Combination method (requires use of two of the following):

- diaphragm with spermicide (cannot be used in conjunction with cervical cap/spermicide)
- cervical cap with spermicide (nulliparous women only)
- contraceptive sponge (nulliparous women only)
- male condom or female condom (cannot be used together)
- hormonal contraceptive: oral contraceptive pill (estrogen/progestin pill or progestin-only pill), contraceptive skin patch, vaginal contraceptive ring, or subcutaneous contraceptive injection

†Abstinence (relative to heterosexual activity) can be used as the sole method of contraception if it is consistently employed as the subject's preferred and usual lifestyle and if considered acceptable by local regulatory agencies and ERCs/IRBs. Periodic abstinence (e.g., calendar, ovulation, sympto-thermal, post-ovulation methods, etc.) and withdrawal are not acceptable methods of contraception.

‡If a contraceptive method listed above is restricted by local regulations/guidelines, then it does not qualify as an acceptable method of contraception for subjects participating at sites in this country/region.

Subjects should be informed that taking the study medication may involve unknown risks to the fetus (unborn baby) if pregnancy were to occur during the study. In order to participate in the study subjects of childbearing potential must adhere to the contraception requirement (described above) from the day of study medication initiation (or 14 days prior to the initiation of study medication for oral contraception) throughout the study period up to 120 days after the last dose of trial therapy. If there is any question that a subject of childbearing potential

will not reliably comply with the requirements for contraception, that subject should not be entered into the study.

### **5.7.3 Use in Pregnancy**

If a subject inadvertently becomes pregnant while on treatment with pembrolizumab, the subject will immediately be removed from the study. The site will contact the subject at least monthly and document the subject's status until the pregnancy has been completed or terminated. The outcome of the pregnancy will be reported to the Sponsor and to Merck without delay and within 24 hours to the Sponsor and within 2 working days to Merck if the outcome is a serious adverse experience (e.g., death, abortion, congenital anomaly, or other disabling or life-threatening complication to the mother or newborn).

The study investigator will make every effort to obtain permission to follow the outcome of the pregnancy and report the condition of the fetus or newborn to the Sponsor. If a male subject impregnates his female partner the study personnel at the site must be informed immediately and the pregnancy reported to the Sponsor and to Merck and followed as described above and in Section 7.2.2.

### **5.7.4 Use in Nursing Women**

It is unknown whether pembrolizumab is excreted in human milk. Since many drugs are excreted in human milk, and because of the potential for serious adverse reactions in the nursing infant, subjects who are breast-feeding are not eligible for enrollment.

## **5.8 Subject Withdrawal/Discontinuation Criteria**

Subjects may withdraw consent at any time for any reason or be dropped from the trial at the discretion of the investigator should any untoward effect occur. In addition, a subject may be withdrawn by the investigator or the Sponsor if enrollment into the trial is inappropriate, the trial plan is violated, or for administrative and/or other safety reasons. Specific details regarding discontinuation or withdrawal are provided in Section 7.1.4 – Other Procedures.

A subject must be discontinued from the trial for any of the following reasons:

- The subject or legal representative (such as a parent or legal guardian) withdraws consent.
- Confirmed radiographic disease progression

*Note:* For unconfirmed radiographic disease progression, please see Section 5.2.2

*Note:* A subject may be granted an exception to continue on treatment with confirmed radiographic progression if clinically stable or clinically improved, please see Section 7.1.2.7.1

- Unacceptable adverse experiences as described in Section 5.2.1.2

- Intercurrent illness that prevents further administration of treatment
- Investigator's decision to withdraw the subject
- The subject has a confirmed positive serum pregnancy test
- Noncompliance with trial treatment or procedure requirements
- The subject is lost to follow-up
- Completed 24 months of uninterrupted treatment with pembrolizumab or 35 administrations of study medication, whichever is later.

*Note: 24 months of study medication is calculated from the date of first dose. Subjects who stop pembrolizumab after 24 months may be eligible for up to one year of additional study treatment if they progress after stopping study treatment provided they meet the requirements detailed in Section 7.1.5.5*

- Administrative reasons

The End of Treatment and Follow-up visit procedures are listed in Section 6 (Protocol Flow Chart) and Section 7.1.5 (Visit Requirements). After the end of treatment, each subject will be followed for 30 days for adverse event monitoring (serious adverse events will be collected for 90 days after the end of treatment as described in Section 7.2.3.1). Subjects who discontinue for reasons other than progressive disease will have post-treatment follow-up for disease status until disease progression, initiating a non-study cancer treatment, withdrawing consent or becoming lost to follow-up. After documented disease progression each subject will be followed by telephone for overall survival until death, withdrawal of consent, or the end of the study, whichever occurs first.

### **5.8.1 Discontinuation of Study Therapy after CR**

Discontinuation of treatment may be considered for subjects who have attained a confirmed CR that have been treated for at least 24 weeks with pembrolizumab and had at least two treatments with pembrolizumab and at least 80% of the planned doses of EBRT beyond the date when the initial CR was declared. Subjects who then experience radiographic disease progression may be eligible for up to one year of additional treatment with pembrolizumab via the Second Course Phase at the discretion of the investigator if no cancer treatment was administered since the last dose of pembrolizumab, the subject meets the safety parameters listed in the Inclusion/Exclusion criteria, and the trial is open. Subjects will resume therapy at the same dose and schedule at the time of initial discontinuation. Additional details are provided in Section 7.1.5.5.

### **5.9 Subject Replacement Strategy**

Additional subjects may be enrolled to ensure that the required number of evaluable subjects is achieved in the applicable analysis population.

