### **8.0 STATISTICAL ANALYSIS PLAN**

#### **8.1 Statistical Analysis Plan Summary**

This is an investigator initiated, open label, phase II clinical trial to evaluate the efficacy of the combination therapy of Pembrolizumab and fractionated external beam radiotherapy (EBRT) in patients with relapsed and refractory aggressive Non-Hodgkin lymphoma (NHL). The maximum number of patients that will be recruited for the study is 40.

The primary objective of the trial is to determine the overall response rate of Pembrolizumab and fractionated EBRT in patients with relapsed and refractory NHL. The secondary objectives are to evaluate the safety, CRR, PFS, OS and duration of response of pembrolizumab with concurrent fractionated EBRT. Patients will receive 200 mg IV of Pembrolizumab with concurrent EBRT at standard of care doses of 40-50 Gy of EBRT in fractions of  $\leq 3$  Gy.. The trial enrollment will be stratified according to the extent of relapsed/refractory disease included in the RT field(s) with 2 cohorts of patients enrolled based on the treated RT field. For Cohort 1, patients with aggressive NHL, will receive RT to 1-2 region(s) of disease and the ORR will be determined for a designated “unirradiated” lesion (Cohort 1). For patients with relapsed/refractory aggressive NHL in Cohort 2, RT will be administered to encompass all sites of radiographically evident disease in 1-2 RT plan(s), the ORR will be based on the disease treated within the RT field. **The maximum number of patients in each cohort is 20 with a total anticipated trial enrollment of 40 patients..**

Overall response rates to PD-1 blockade monotherapy among patients with hematologic malignancies is based on published data. For cohort 1, we assume that concurrent external beam radiation therapy with concurrent pembrolizumab will improve ORR (of the non-irradiated lesion[s]) over the reported rates of PD-1 blockade which are roughly 26% for B cell lymphoma and 17% for T cell lymphoma.

**While the ORR for definitive RT for patients with de novo aggressive NHL approach 100%, overall response rate to salvage RT for patients with refractory aggressive NHL treated with curative intent has been reported to be 78%, with a 5 year progression free survival rate of 34%. We assume that concurrent EBRT and pembrolizumab will improve the ORR when all sites of known disease are radiated.**

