#### **8.2 Statistical Analysis Plan**

Phase II design:

The overall response (OR: complete response + partial response) of non-irradiated lesion(s) at three months and dose limiting toxicity (DLT) at one cycles (3 weeks) will be monitored simultaneously using the Bayesian stopping boundaries calculated based on beta-binomial distributions. Independence is assumed between OR and DLT.

DLT is defined as the following toxicities observed during cycle one of the treatment that are considered by the investigator to be related to therapy:

1. Grade 4 neutropenia (ANC < 500/mm3) lasting more than 7 consecutive days.
2. Grade 3 neutropenia with fever and/or infection, where fever is defined as an oral Temperature  $\geq 38.5^{\circ}\text{C}$ .
3. Grade 4 thrombocytopenia (platelets < 25,000/mm3) lasting more than 7 consecutive Days.
4. Grade 3 thrombocytopenia with clinically significant bleeding.
5. A platelet count < 10,000/mm3 at any time.
6. Grade 3 or greater nausea and/or emesis despite the use of optimal anti-emetic Prophylaxis. Optimal anti-emetic prophylaxis is defined as an anti-emetic regimen that employs a 5-HT3 antagonist given in standard doses and according to standard schedules.
7. Grade 3 or greater diarrhea that occurs despite maximal supportive therapy.
8. Any other Grade 3 or greater non-hematologic toxicity with the following exceptions: Grade 3 arthralgia/myalgia or brief (< 1 week) Grade 3 fatigue.
9. A delay of more than 2 weeks in the initiation of Cycle 2 of treatment because of a lack of adequate recovery of therapy related hematological or non-hematologic toxicities.

In cohort 1 for the patients with multiple sites of aggressive NHL, we will consider that the regimen is promising if the OR rate of the non-irradiated lesion (s) at 3 months is at least 35% and the DLT rate at cycle one is below 30%. A sample size of 20 ensures that, if the trial is not terminated early, a posterior 90% credibility interval for OR rate at 3 months will have width of 0.335 at most, when 7 responses are observed out of the 20 patients, under the assumption of 35% OR rate. The prior probability of OR and DLT for the regimen are modeled by beta distribution ( $\text{Beta}(0.35, 0.65)$  and  $\text{Beta}(0.3, 0.7)$ , respectively). Denoting the probability of OR and DLT by  $\{\theta_{\text{OR}}, \theta_{\text{DLT}}\}$ , and they are compared to fixed targets of OR and DLT rates. The following decision criteria will be applied:

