- 1) Stop if  $\text{Prob}\{\theta_{\text{OR}} < 0.35 \mid \text{data}\} > 0.95$ , and
- 2) Stop if  $\text{Prob}\{\theta_{\text{DLT}} > 0.30 \mid \text{data}\} > 0.95$

Patients will be monitored by a cohort size of 10 according to the following stopping boundaries for OR at 3 months and DLT at cycle one. If the number of responses required for moving the trial to next stage has not been achieved, the patient enrollment will be halted until enough responses observed.

Number of patients evaluated	Stop if <= OR observed	Stop if >= DLT observed
10	0-1	6-10
20	Always stop with this many patients	

The operating characteristics are summarized in the following table (based on simulations from 10,000 trials).

True DLT Rate	True OR Rate	Prob (stop the trial early)	Average number of patients treated
0.1	0.15	0.5444	14.56
	0.25	0.2441	17.56
	0.35	0.0861	19.14
	0.45	0.0234	19.77
	0.55	0.0046	19.95
0.2	0.15	0.5472	14.53
	0.25	0.2488	17.51
	0.35	0.0918	19.08
	0.45	0.0295	19.71
	0.55	0.0108	19.89
0.3	0.15	0.5659	14.34
	0.25	0.2798	17.20
	0.35	0.1292	18.71

	0.45	0.0695	19.31
	0.55	0.0516	19.48
0.4	0.15	0.6201	13.80
	0.25	0.3697	16.30
	0.35	0.2379	17.62
	0.45	0.1856	18.14
	0.55	0.1700	18.30
0.5	0.15	0.7161	12.84
	0.25	0.5290	14.71
	0.35	0.4305	15.69
	0.45	0.3914	16.09
	0.55	0.3798	16.20

In cohort 2 patients will be treated to all sites of relapsed or refractory NHL that can be completely included in 1-2 RT field(s), we will consider that the regimen is promising if the OR rate of the radiated disease at 3 months is at least 90% and the DLT rate at cycle one is below 30%. A sample size of 20 ensures that, if the trial is not terminated early, a posterior 90% credibility interval for OR rate at 3 months will have width of 0.203 at most, when 18 responses are observed out of the 20 patients, under the assumption of 90% OR rate. The prior probability of OR and DLT for the regimen are modeled by beta distribution (*Beta*(0.9,0.1) and *Beta*(0.3,0.7), respectively). Denoting the probability of OR and DLT by  $\{\theta_{OR}, \theta_{DLT}\}$ , and they are compared to fixed targets of OR and DLT rates. The following decision criteria will be applied:

- 1) Stop if  $\text{Prob}\{\theta_{OR} < 0.90 \mid \text{data}\} > 0.95$ , and
- 2) Stop if  $\text{Prob}\{\theta_{DLT} > 0.30 \mid \text{data}\} > 0.95$

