## ANALYSIS PLANS

For each patient cohort, summary statistics will be provided for continuous variables such as age. Frequency tables will be used to summarize categorical variables such as gender, histology, response, toxicity type and severity. Response rate and its 95% confidence interval will be estimated for each patient cohort separately. The distribution of time-to-event endpoints, such as time to progression and overall survival, will be estimated using the method of Kaplan and Meier. Comparison of time-to-event endpoints by important patient characteristics will be made using the log-rank test.

Time-to-event outcomes, including PFS and OS will be estimated using the Kaplan-Meier method, with analysis beginning at the receipt of the first dose of MK-3475. The log-rank test will be performed to test the difference in time-to-event distributions between patient groups. Cox proportional hazards model may be used to include multiple covariates in the time-to-event analysis.

Assuming an accrual rate of 2 patients per month, we anticipate an accrual period of roughly 20 months. Data from all subjects who receive any study drug will be included in the safety

analyses. Subjects who entered the study and did not take any of the study drug and had this confirmed, will not be evaluated for safety.

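### Section 5.9 allows enrolment to continue until enough undefined 'evaluable' subjects are reached, so treated patients without a response assessment may drop out of the primary response rate, and the rule conflicts with the enrolment caps

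*Combined protocol and SAP*

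**What the plan says.** - **Replacement (5.9).** The whole section is one sentence: "Additional subjects may be enrolled to ensure that the required number of evaluable subjects is achieved in the applicable analysis population". The supplied text does not define evaluable, say who may be replaced, or name an efficacy population.
- **Monitoring (8.2).** In both cohorts the stopping table is indexed by "Number of patients evaluated", with one look at 10 and a final count of 20. If too few responses are seen, "the patient enrollment will be halted until enough responses observed".
- **Precision (8.2).** The interval widths are stated for Cohort 1 "when 7 responses are observed out of the 20 patients" and for Cohort 2 "when 18 responses are observed out of the 20 patients". Neither statement says whether the 20 are treated or evaluable.
- **Analysis (Analysis Plans).** "Response rate and its 95% confidence interval will be estimated for each patient cohort separately", with no denominator and no rule for a missing assessment. By contrast, "Data from all subjects who receive any study drug will be included in the safety" analyses.
- **Caps (8.1).** "The maximum number of patients in each cohort is 20 with a total anticipated trial enrollment of 40 patients"; the same section limits recruitment to 40. Section 5.3 gives n=20 per cohort. The accrual forecast in Analysis Plans (2 per month for 20 months) is also 40, with no reserve. The Trial Summary in section 1.0 lists 21 subjects.

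**The concern.** OR at 3 months is the primary endpoint. It drives the futility stop at 10 patients and is judged against 35% in Cohort 1 and 90% in Cohort 2. A patient who dies early without a scan, withdraws or is lost to follow-up is probably less likely than average to have responded. If such patients can be replaced by others who reach a scan, the denominator is selected on something related to outcome, and OR is biased upward to the extent that those replaced are non-responders. With 10 patients at the look and 20 at the end, one replacement can decide which side of a boundary the result falls on.

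The caps create a second problem. The design runs to 20 evaluated patients per cohort, while 8.1 allows at most 20 enrolled. One unevaluable patient leaves 19 evaluated, or takes the cohort to 21 if 5.9 is used.

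**Working it through.** **1. Reproduce the plan.** The priors are Beta(0.35, 0.65) for Cohort 1 OR and Beta(0.9, 0.1) for Cohort 2 OR (8.2).

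- 90% equal-tailed interval at 7/20: posterior Beta(7.35, 13.65), 0.191 to 0.526, width 0.335 (plan 0.335).
- 90% equal-tailed interval at 18/20: posterior Beta(18.9, 2.1), 0.777 to 0.980, width 0.203 (plan 0.203).
- Look at 10, Cohort 1: Prob(OR < 0.35) is 0.971 at 1/10 and 0.865 at 2/10. With the 0.95 threshold this gives the stated boundary of 0-1.
- Look at 10, Cohort 2: Prob(OR < 0.90) is 0.989 at 6/10 and 0.940 at 7/10. This gives the stated boundary of 0-6.
- Early stopping, combining the OR and DLT stops as independent: all 50 table entries agree to within 0.0001. For example, at a DLT rate of 0.1, Cohort 1 with true OR 0.15 gives 0.5444 and Cohort 2 with true OR 0.70 gives 0.3505, both as tabled.

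The stated operating characteristics therefore belong to 10 and 20 patients counted in the OR.

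**2. Effect of one replaced patient at the look.** In Cohort 2, 7 responders among 10 evaluated continues (0.940). If one further treated patient had been replaced and is counted as a non-responder, the data are 7/11, the posterior is Beta(7.9, 4.1), and Prob(OR < 0.90) = 0.984, above 0.95. Cohort 1 is less sensitive: 2/10 continues (0.865), and it takes four replaced non-responders (2/14, 0.964) to pass 0.95.

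**3. Effect on the rate.** Let p be the true OR among all treated patients, f the share of treated patients replaced, and k the response rate of replaced patients relative to evaluable ones. The evaluable-only rate is

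p / ((1 − f) + f·k).

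The documents give no f or k. I assume f = 0.10 and let k run over 1, 0.5 and 0, so the divisor is 1, 0.95 or 0.90. For p I use the reference rates in 8.1: 26% (PD-1 monotherapy, B cell) and 78% (salvage RT alone). The OR-stop probability is the binomial chance of at most 1/10 in Cohort 1 and at most 6/10 in Cohort 2.

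| True OR | k | Evaluable-only OR | OR stop at 10 |
|---|---|---|---|
| Cohort 1, 26% | 1 | 26.0% | 0.222 |
| | 0.5 | 27.4% | 0.195 |
| | 0 | 28.9% | 0.167 |
| Cohort 2, 78% | 1 | 78.0% | 0.159 |
| | 0.5 | 82.1% | 0.087 |
| | 0 | 86.7% | 0.034 |

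At k = 0 in Cohort 2, the chance of observing at least 18/20 (an observed rate of 90%) rises from 0.151 to 0.490.

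**4. Enrolment needed for 20 evaluated per cohort.** This is 20/(1 − q), rounded up, where q is an assumed unevaluable share: q = 5% gives 22, 10% gives 23 and 20% gives 25. Each exceeds the cap of 20.

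**The case against.** A reader might infer that the plan excludes treated but unassessed patients from the OR. It does not say so. Section 5.9 is permissive and fits equally well with replacing only patients who turn out ineligible or never start treatment. That objection stands: exclusion is allowed, not stated.

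The imaging plan also limits how many patients could be unassessed:
- Every patient has a Week 8 scan (sections 2.2, 6.1 and 7.1.2.6.3), and progression at Week 8 is to be re-imaged at least 28 days later.
- The first scan may be brought forward for clinical progression (6.1, note o).
- Imaging is planned at discontinuation and continues off treatment (5.8 and 7.1.2.6.1).

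These provisions capture many early progressors. They do not cover death before any scan, and follow-up ends at withdrawal of consent or loss to follow-up. They also leave open how a patient with only an early scan enters the 3-month OR.

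The halt rule could, on one reading, stop further entry before a replacement is enrolled. On the other, it applies only once 10 patients have been evaluated. The text does not settle which.

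On size, the Cohort 1 shift of at most 2.9 points (28.9 − 26.0) is small beside an interval width of 0.335. Neither worst case in the table reaches its target. That is fair for Cohort 1. In Cohort 2, however, the futility stop loses most of its force in the worst case.

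A reader might also take 5.9 and 8.1 to conflict from the outset. The contradiction arises only when replacement takes a cohort past 20 or the trial past 40. Reading the caps as evaluable patients does not rescue them, because 8.1 speaks of patients recruited and enrolled.

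**Conclusion.** The concern holds in this form: the plan permits, but does not require, outcome-related replacement in the primary OR, and using that permission beyond 20 per cohort or 40 in total contradicts 8.1 and 5.3. The OR denominator and the handling of missing responses should be settled before the look at 10.

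The actual bias cannot be computed. It is zero if missingness is unrelated to response. At an assumed 10% replaced, it is at most 8.7 points in Cohort 2 (86.7 − 78.0) and 2.9 points in Cohort 1, both when none of the replaced patients would have responded. These figures are illustrations of sensitivity, not forecasts. Cohort 2 is the more exposed, because its boundary can turn on a single replaced patient.

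**What to change.** Amend 5.9, 8.1 and 8.2 as follows.

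1. Base interim and final OR in each cohort on all patients who start any study treatment (EBRT on Day 1 or pembrolizumab on Day 2). This set differs from the safety set, which requires study drug, by patients irradiated but never dosed; say so.
2. State which scheduled scan and window supply the 3-month OR. The schedule is Week 8 and then every 3 months (12 weeks in 7.1.2.6.3). If the interval runs from Week 8, the next scan falls at about Week 20 (8 + 12). Without this definition a Week 8 responder could be misclassified.
3. Count patients with no documented response in that window as non-responders, with early progression handled under the existing confirmation provisions.
4. Report the evaluable-only rate, with evaluable defined, as a sensitivity analysis.
5. Limit replacement to patients who never start study treatment.
6. State whether 20 and 40 are enrolled or treated numbers, and reconcile them with 5.3 and with the 21 subjects in the Trial Summary.

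The cost is wording only: the scans, the data and the design size of 20 per cohort stay the same. The downside is that the observed OR may be lower.
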